Conceptual definition. Movement restriction-induction therapy modified (Constraint-Induced Movement Therapy –mCIMT-) is a rehabilitation technique developed by Edward Taub et al., in which the recovery of a limb affected by a brain injury, mainly a CVE, can be induced by immobilizing the intact arm and training the injured arm ²⁶⁻²⁸.

Operational definition. For the purposes of this investigation, a sling will be placed on the healthy thoracic limb so that it can carry out the therapeutic activities indicated in Annex 1 with the sick limb, without any help, not even from the therapist.

Indicators. The therapy will be directed by the same therapist at pre-established times and days and that will be different days than those of the subjects who will receive the other therapies, it will be carried out for 1 hour, 2 times a week, for 6 weeks. The therapy program is shown in Annex 1 with the specific activities that will be standardized for all patients.

Measurement scale. Qualitative, nominal.

Rehabilitation program with regular physical and occupational therapy

Conceptual definition. Physiotherapy (from the Greek φυσις physis, 'nature', and θεραπεία therapéia, 'treatment') is a health discipline that offers a non-pharmacological therapeutic alternative, to alleviate symptoms of multiple ailments, both acute and chronic, through exercise therapeutic, heat, cold, light, water, manual techniques including massage and electricity; and the occupational is the set of techniques, methods and actions that, through activities applied for therapeutic purposes, prevents disease and maintains health, favors the restoration of function, makes up for disabling deficiencies and assesses the assumptions of behavior and its deep significance to achieve the greatest possible independence and reintegration of the individual in all its aspects: work, mental, physical and social.

Operational definition. In the present investigation, a "usual" program has been developed in the rehabilitation unit where the work will be carried out. They are a series of standardized and individualized activities according to the state of the subject. For study purposes, the programs are presented in Annex 1, and will be provided without the support of virtual reality or the restriction-induction technique of movement.

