1. Patients who develop dementia or neurological-psychomotor complications during the study.
2. Patients who present a new cerebrovascular event during the investigation
3. Patients who do not complete at least 90% of the program
4. Patients in whom a lack of family support or secondary gain is detected.

STUDY TYPE AND DESIGN

Type study

Clinic

Design Study

Controlled clinical trial, randomized, single-blind.

MATERIAL AND METHODS

Population

Adult patients with a clinically and tomography-confirmed diagnosis of a Cerebral Vascular Event, with body hemiparesis, with or without aphasia.

Geographic scope

Outpatient services and physical/occupational therapy of the Physical Medicine and Rehabilitation Unit XXI Century (PMRUcXXI). Southern Delegation of the Federal District, IMSS.

Limits in time

March 2020 to June 2024.

Study General description

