After working on this task for a while, I felt quite competent.									
Effort and importance of treatment									
I felt it was my choice to do the task.									
I didn't really have the option to do task (R).									
I felt like I was doing what I wanted to do while working on the assignment.									
I felt that I had obligation to do task (R)									
I did the homework because I had no other option (R).									
Stress or strain (caused by treatment)									
I didn't feel nervous about doing task (R).									
I felt tense while doing task.									
I felt relaxed while doing task (R).									
I was anxious while doing task.									
I felt stressed while doing task.									

Ini. Val.: initial valoration; Intermed. Val.: intermediate valoration; Fin. Val.: final valoration.

Subscale scores can be used as dependent variables, predictors, or mediators, depending on the research questions being addressed. The higher the score, the higher the satisfaction.

3. Therapy programs.

- a. Virtual reality program. The activities indicated in the tennis and ski software for the upper limb, covering cracks for both limbs and Star Wars-battles in the galaxy for the hand and fine pincer,

which will be carried out with the interface of the virtual reality equipment "connected" to the patient through movement sensors, with the multiperceptual feedback of the Kinect equipment or with googles.

b. *Movement restriction and induction therapy.* The patient will be placed a sling on the "healthy" thoracic limb, attached to the thorax, through a bra, gently but firmly, in such a way that it does not alter circulation or compress peripheral nerves. It will be explained to you that you should do all your activities with the "sick" member, to the extent possible. The restriction of the healthy side forces the patient to put all his effort into carrying out the activities of daily life, simulated during the therapy. This restriction will be carried out for 1 hour in therapy in the medical unit. And the patient will be told to repeat it at home at least once a day for one to five hours, without receiving support from family members while wearing the sling.

c. *Regular physical and occupational therapy.* The specific activities are shown in Annex 1. They include:

- **Motor management:** tasks to promote mobility of the shoulder, elbow, pentadigital clamp, fine clamp, transfers; volitional movements, eye-motor coordination, hip, knee, ankle and gait mobility.

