- **Sensory training:** deep sensitivity, stereognosis, sensory discrimination, graphesthesia, topognosis and proprioception.

4. *Concentration and analysis of information.* The results of the different evaluations will be noted on the information capture sheet (Annex 2 and 4); Subsequently, they will be entered into an Excel spreadsheet and finally exported for analysis to the SPSS V-19 program.

STATISTICAL ASPECTS

Sampling

Non-probabilistic, of consecutive cases.

Sample size

The sample size calculation was performed to test the working hypothesis* (average difference of 38.6 points and a SD 12.23), with a standardized effect size greater than 1 in a prefabricated table to establish mean differences (Appendix 1. 13 -A)⁵², considering a unilateral hypothesis, in a finite population and without replacement, with a value $\alpha = 0.05$ and $\beta = 0.10$.

For 17 patients plus 20% of possible losses, for a total of 19 patients per group.

* The score of the motor evolution evaluated with the Fugl-Meyer scale was considered, with therapy supported by virtual reality, found in the study of the unit, considered as a pilot^{47, 48}.

Statistic analysis

Descriptive statistics will be carried out for the qualitative variables through tables, graphs and percentages; for the quantitative ones, measures of central tendency and its corresponding dispersion will be used, depending on the distribution of the data. The distribution of the numerical data will be compared with the distribution curve using the Shapiro-Wilk test, depending on the result, the ANOVA or Friedman test will be used for intragroup comparison; for comparison between groups, ANOVA of repeated measures or the Kruskal-Wallis test will be used. In case of detecting variables that could be potentially related to the result, correlation tests such as Pearson or Spearman will be applied. An α value of 0.05 will be considered.

ETHICAL ASPECTS

This research respects the institutional, national and international standards that govern research on human beings in our country. Including the General Health Law, TITLE FIVE Research for Health, sole chapter ⁵³; the regulation of the General Law of Health in Matters of Research for Health ⁵⁴; and the Official Mexican Standard NOM-012-SSA3-2012, which establishes the criteria for the execution of research projects for health in human beings ⁵⁵.

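### The visible forms have no dedicated field for adverse events or home sling hours, and no harm table by arm is planned, although the restriction arm takes a sling home soon after stroke

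*Combined protocol and SAP*

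**What the plan says.** **Data flow.** Procedures 4 (Concentration and analysis of information) states that "The results of the different evaluations will be noted on the information capture sheet (Annex 2 and 4", after which the data go to a spreadsheet and to SPSS. Annex 2 holds the Fugl-Meyer scale, Motor Index, fine clamp test, Boston aphasia scale and Intrinsic Motivation Inventory. Annex 4 holds identification, history, diagnosis, examination, treatment group, Ashworth and Brunnstrom. The Statistic analysis section names no safety outcome and no harm table.

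**The sling.** Procedures 3b has it fitted to the healthy arm "in such a way that it does not alter circulation or compress peripheral nerves". The instruction for the time after the supervised hour reads: "repeat it at home at least once a day for one to five hours, without receiving support from family members while wearing the sling". The operational definition of this therapy adds that tasks are done "without any help, not even from the therapist". Inclusion criterion 4 limits entry to one month from the stroke.

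**Events during the study.** The Elimination criteria remove "Patients who develop dementia or neurological-psychomotor complications during the study", "Patients who present a new cerebrovascular event during the investigation" and "Patients who do not complete at least 90% of the program". They do not ask for a count or a reason by arm.

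**Risk class.** Ethical aspects classes the study as above minimum risk.

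**The concern.** The three arms would be compared on motor change, language and satisfaction with no planned count of harms beside them. The protocol gives its own reasons to count. Its background names falls and pain as common after stroke, Procedures 3b names the sling hazard, and most of the sling time may fall at home. The most serious foreseeable events, a new stroke or a neurological complication, appear only as grounds for taking a patient out, so they could leave the results without being reported.

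Harms that were never asked about cannot be restored at the analysis stage. The Transcendence section hopes for uptake in other units and points to virtual reality equipment in private homes. The planned data would say little about safety in such use.

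**Working it through.** **1. What the forms capture.** Read against the events that matter here:

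| Event or exposure | Annex 2 | Annex 4 |
|---|---|---|
| Fall | no field | no field |
| Numbness, skin or circulation problem of the slung arm | no field | no field |
| New vascular event, hospital contact, death | no field | no field |
| Home sling hours | no field | no field |
| Joint pain (Fugl-Meyer) | three visits | – |
| Treatment-caused stress (motivation inventory) | three visits | – |
| Muscle tone (Ashworth) | – | three visits |

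The last three rows are partial signals, but they are scale scores and none is designated a safety outcome. Annex 4 also has open lines for a clinical summary and physical examination. Physician 1 completes that sheet at entry (Procedures 1), and only Ashworth and Brunnstrom have columns for later visits.

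**2. Sling exposure per patient.** Inputs: 12 sessions of 1 hour over 6 weeks, and home wear of 1 to 5 hours at least once a day (Procedures 3b). Assumption: home wear once a day for 6 × 7 = 42 days. The protocol does not state the number of days.

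- Supervised: 12 × 1 = 12 h.
- Home at 1 h a day: 42 × 1 = 42 h, which is 42/(42 + 12) = 78% of sling time.
- Home at 5 h a day: 42 × 5 = 210 h, which is 210/(210 + 12) = 95%. This is not a ceiling, because the instruction is for at least once a day.
- At half compliance: 21 h, or 21/33 = 64%, to 105 h, or 105/117 = 90%.

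For an arm of 19 at full compliance, home time is 19 × 42 = 798 h to 19 × 210 = 3,990 h, against 19 × 12 = 228 h supervised.

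**3. Which arm wears the sling.** The operational definition and Procedures 3b put it in the restriction arm. The summary under Material and methods reverses this and immobilises the healthy arm in usual therapy. Annex 1, the shared program, specifies a sling in its three seated training blocks. Supervised sling use may therefore occur in two arms, but the home instruction is given only for the restriction arm.

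**4. What 19 per arm can show.** The plan has no figure for harms; its only planning figure is group size. The Appendix 1 table gives 17 per group at a standardised effect of 1.00, one-sided α = 0.05 and β = 0.10. The normal approximation gives 2 × (1.645 + 1.282)² = 17.1, rounded up to 18, which agrees closely. The plan then states 19 after losses, and that figure is used here.

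- Zero events in 19: one-sided 95% upper bound 1 − 0.05^(1/19) = 14.6%. In 17: 1 − 0.05^(1/17) = 16.2%.
- One event in 19: 1/19 = 5.3%, exact 95% interval 0.1% to 26.0%.
- Chance of at least one event in 19, at assumed true risks (the protocol gives none): 1 − 0.95^19 = 62% at 5%, and 1 − 0.90^19 = 86% at 10%.

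A simple count would probably reveal a fairly common harm. It could not rule one out.

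**The case against.** The strongest reply is that events have a route to the record. One treating physician monitors the patients, answers their questions throughout and keeps the clinical file (Procedures 1). New strokes and neurological complications must be identified in every arm for the elimination criteria to be applied. Selection also limits risk: age 35 to 70, limited spasticity, no cognitive deficit and no uncontrolled comorbidity. The protocol cites national research rules and had ethics approval, the consent form (Annex 3) is not in the copy reviewed, and the techniques are described as moderate exercise.

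Much of this stands. Reporting duties and consent wording cannot be judged. It does not supply a structured question, a transfer to the data set or a tabulation.

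Four stronger readings are tempting, and the documents do not support them:

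- *Home wear and harms go unrecorded altogether.* The forms show only that there is no dedicated field. The clinical file may hold some of this information.
- *Harms would be ascertained differently by arm.* The treating physician is a channel common to all arms, and nothing suggests that it works differently among them.
- *Patients are left alone at home in a sling.* Set beside the rule against help from the therapist, and the elimination of "Patients in whom a lack of family support or secondary gain is detected", the wording bars help with the tasks. It does not say that nobody is present.
- *The joint-pain items cannot concern the slung arm.* Procedures 1 refers to evaluating the affected side of the body, but the pain items name no side, and the scale has balance items for the unaffected side. The side is an inference.

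**Conclusion.** The point holds as a gap in collection and reporting, and closing it is a worthwhile, inexpensive improvement. The visible forms have no dedicated field for adverse events or home sling hours, and no harm table by arm is planned, in a study that its own protocol rates above minimum risk. Home sling time is 42 h, or 210 h at five hours a day, against 12 supervised hours per patient, if wear is daily for 42 days. That rests on following the detailed sections rather than the summary about which arm wears the sling. The hours measure exposure and say nothing about how often harm occurs. The efficacy analysis is not affected.

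**What to change.** Add a short harms block to Annex 4, on a separate page, completed at each session by the therapist or physician 1 and kept from evaluator 2. Ask the same questions in all three arms, covering the session and home time since the last visit:

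- fall;
- new limb pain on either side;
- numbness or skin change of either arm;
- new vascular event or hospital contact;
- death;
- recalled home sling hours, where a sling is used.

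Identical questions in every arm work whichever description of sling use is followed.

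Report descriptive counts by randomised arm for all randomised patients, including those removed under the Elimination criteria, with the reason. For patients already treated, extract events from the clinical file and label them as such.

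**Cost.** At most 3 × 19 × 12 = 57 × 12 = 684 brief records, one descriptive table and a file review. There will be fewer records if patients have already been treated, which is likely given the stated time limits of March 2020 to June 2024. The sample size does not change.

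**Downsides.** Unblinded staff complete the block, evaluator 2's blinding needs protecting, home hours rely on recall, file extraction will be incomplete, and the counts cannot show that an arm is safe.

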uses electronic equipment to reveal to the individual some of the normal or abnormal physiological events, in the form of auditory or visual signals, teaching him to manipulate involuntary events through displayed signals. Several studies show that the movement of the upper and lower limbs together with a specific objective translates into greater motor learning at the cortical level and therefore greater movement recovery. Biofeedback supported by computer systems (Virtual Reality) allows the total immersion of the patient in a "real" environment where he receives sound, visual and tactile sensory information, which produces a multimodal environment. Recent research on motor recovery in paretic limbs with the use of virtual reality shows an encouraging improvement, in addition to showing greater adherence due to the associated playful factor, which allows more treatment time without costs for health systems.

According to some meta-analyses, the multiple existing publications related to these 2 types of therapies have been carried out in small populations, without considering demographic variants, affected brain territory or severity of the condition, among others, which has caused them to be considered inconsistent and of little cost-benefit utility to be introduced in the rehabilitation units. That is why research on these "new" therapies continues to be carried out, seeking methodological support and consistent results, both clinical and cost.

Research Question.

What is the effect of different therapeutic modalities supported by Virtual Reality or Restriction and Induction of Movement compared with usual Physical and Occupational Therapy on motor recovery of paretic limbs in patients with Cerebrovascular Event?

Secondary questions

1. To determine the relationship between the therapeutic management group and motor evolution with changes in language (aphasia).
2. To measure the level of patient satisfaction with the treatment received.
3. To relate the level of patient satisfaction with adherence to treatment.

Hypothesis.

A therapeutic program supported in virtual reality will increase the motor function of the paretic thoracic extremity of patients with CVE by at least 38.6** average points measured with the Fugl Mayer scale compared with usual physical and occupational therapy.

Aim.

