Similarly, studies carried out in our country have shown the advantages of virtual reality as support in the rehabilitative management of patients with CVE. Although the improvement has been insignificant in different measurements, a positive emotional component and better adherence to treatment are frequently described. In a study carried out at the National Institute of Neurology and Neurosurgery (INNN) an increase in the score measured with the Fugl-Meyer scale was found in patients managed with virtual reality (-initial- 13.41 to 31.91 -final-) compared to the group who received habitual occupational therapy (18 to 26.3); when measuring motor changes with the Motor Index, the findings were similar (virtual reality from 32.33 to 52.91 -initial/final- compared to the control group from 42.1 to 52.6 -initial/final-). Changes in patient satisfaction were measured with the intrinsic motivation inventory, and those who underwent virtual reality therapy were more satisfied than the group with only therapy ³⁴.

As described in some reviews and meta-analyses, many studies focus only on the upper limb and/or the hand, perhaps because they are the most frequently difficult to recover or show sequelae even over time. In another study conducted in Korea, only the upper limb was managed and evaluated; in it, functionality was evaluated with the Fugl-Meyer scale and the modified Barthel index. However, as

can be seen in the following table, the differences between the groups were only significant in hand scores, while the intragroup changes were significant in all evaluations ⁴⁴.

Variations between groups pre and post intervention.

	FMA (score)								K-MBI (score)	
	Arm		Wrist		Hand		CS		Total	
	Pre	Post	Pre	Post	Pre	Post	Pre	Post	Pre	Post
MCAG (n=6)	17.8±9.7	22.8±6.8 ^a	5.3±3.4	5.5±3.6	8.2±4.7	9.0±5.1 ^a	3.3±0.8	3.8±0.8	81.5±5.4	83.3±5.4 ^a
BGG (n=8)	21.0±4.5 ^b	27.5±4.7 ^a	5.6±1.6	6.9±1.6 ^a	7.9±2.6 ^b	11.9±2.5 ^{ab}	3.8±0.9	4.6±0.7 ^a	79.6±8.2	82.0±8.1 ^a

A lowercase “a” indicates a significant intragroup difference and “b” indicates a significant difference between groups. FMA = Fugl-Meyer scale. K-MBI = Korea Modified Barthel Index. CS = coordination and speed. MCAG = middle cerebral artery group. BGG = basal ganglia group.

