What is the effect of different therapeutic modalities supported by Virtual Reality or Restriction and Induction of Movement compared with usual Physical and Occupational Therapy on motor recovery of paretic limbs in patients with Cerebrovascular Event?

Secondary questions

1. To determine the relationship between the therapeutic management group and motor evolution with changes in language (aphasy).
2. To measure the level of patient satisfaction with the treatment received.
3. To relate the level of patient satisfaction with adherence to treatment.

WORK HYPOTHESIS

A therapeutic program supported in virtual reality will increase the motor function of the paretic thoracic extremity of patients with CVE by at least 38.6** average points measured with the Fugl-Meyer scale compared with usual physical and occupational therapy.

**The smallest difference in the improvement of the hemiparesis function calculated in points with the Fugl Meyer scale, found in patients with characteristics similar to those of the patients in this protocol, was taken. As well as the lowest standard deviation to cover all values^{46, 47}.

AIM

To measure the effect of different therapeutic modalities supported by Virtual Reality or Restriction and Induction of Movement compared with usual Physical and Occupational Therapy on the motor recovery of paretic limbs in patients with a Cerebral Vascular Event.

VARIABLES

Independent Variable

Cerebral vascular event

Conceptual definition. It is defined as a clinical syndrome characterized by the rapid development of signs and/or symptoms usually corresponding to a focal or global neurological condition (applicable to patients with loss of consciousness or acute headache), which persist for more than 24 hours or which lead to death, with no other apparent cause than a vascular origin" ^{1, 2}.

Operational definition. In this work, the patient who comes to request care at the outpatient clinic of the UMFR sXXI will be considered, with the interconsultation format 4-30/8 where it is indicated that the patient suffered a cerebral vascular event and who presents neurological data consistent with the diagnosis, mainly hemiparesis, with or without aphasia. The verification of the diagnosis will be made later in the office, with the support of the computed tomography and verified during the physical examination; It will also be verified that it covers the rest of the selection criteria.

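### The 38.6 Fugl-Meyer points given as the virtual reality versus usual therapy difference match the pilot control group's final mean; the 17 per group rests on one SD (12.23 points), and 17 plus 20% is not 19

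*Combined protocol and SAP*

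**What the plan says.** The Hypothesis in the summary and the Work Hypothesis in the body both state that VR will raise upper-limb motor function "by at least 38.6 average points measured with the Fugl-Meyer scale compared with usual physical and occupational therapy". The Sample size section repeats the figure: "average difference of 38.6 points and a SD 12.23), with a standardized effect size greater than 1". It uses a one-sided hypothesis with alpha 0.05 and beta 0.10, and reads the size from a published table reproduced as Table 13.A in Appendix 1. The result is: "For 17 patients plus 20% of possible losses, for a total of 19 patients per group".

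Two footnotes explain where 38.6 comes from. Under Work Hypothesis it is described as "The smallest difference in the improvement of the hemiparesis function" in comparable patients, and the SD is described with the words "As well as the lowest standard deviation to cover all values". Under Sample size the source is given differently: "The score of the motor evolution evaluated with the Fugl-Meyer scale was considered, with therapy supported by virtual reality", taken from the unit's own study, which is treated as a pilot. Table 1 summarises that pilot experience.

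**The concern.** An effect of 38.6 points against an SD of 12.23 is more than three SDs, which is very large for one rehabilitation programme compared with another. The same number appears in Table 1 as a group mean, and the two footnotes give different origins for it. If the figure is a mean mislabelled as a difference, the plan's only numerical hypothesis states an effect that its own pilot data do not show, and a reader cannot tell from the text what difference the sample size was chosen to detect. The addition of losses also fails as simple arithmetic. That matters because the Elimination criteria remove patients who complete less than 90% of the programme (0.9 x 12 = 10.8, so fewer than 11 of 12 sessions).

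**Working it through.** **Inputs.** Table 1, Fugl-Meyer row:

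| Group | Initial (SD) | Final (SD) | Change |
|---|---|---|---|
| VR (n=13) | 28.31 (12.02) | 41.07 (9.28) | 12.77 |
| Restriction and induction (n=23) | 9.34 (3.7) | 11.27 (2.67) | 1.93 |
| Therapy alone (n=10) | 27.70 (12.23) | 38.60 (11.8) | 10.9 |

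Sample size section: difference 38.6, SD 12.23, one-sided alpha 0.05, beta 0.10, 17 per group, 20% losses, 19 per group.

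**1. Reproducing 17.** Table 13.A ends at E/S = 1.00, where one-sided 0.05 and beta 0.10 give 17. The normal-approximation formula agrees: 2 x (1.645 + 1.282)^2 / 1^2 = 17.1. So 17 reproduces at a difference of one SD, 1.00 x 12.23 = 12.23 points.

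**2. What 38.6 would need.** E/S = 38.6 / 12.23 = 3.16. The formula gives 17.1 / 3.16^2 = 1.7, that is, 2 per group. By the noncentral t distribution, power is 65% with 2 per group and 93% with 3. The stated difference therefore needs about 3 per group, not 17.

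**3. Where 38.6 comes from.** It equals the therapy-alone final mean (38.60), and 12.23 is the same group's initial SD. The pilot's VR-minus-therapy-alone differences are:
- change: 12.77 - 10.9 = 1.87 points (0.15 of SD 12.23);
- final score: 41.07 - 38.60 = 2.47 points (0.20 of SD 12.23).

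Neither footnote fits. The smallest VR-versus-control difference in improvement in Table 1 is not 38.6, and the VR scores are 28.31 and 41.07. The two footnotes also disagree with each other.

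**4. Losses.** Adding 20%: 17 x 1.2 = 20.4, so 21. Allowing for 20% lost: 17 / 0.8 = 21.25, so 22. Nineteen corresponds to 1 - 17/19 = 10.5% losses. If 20% of 19 are lost, 19 x 0.8 = 15.2, about 15 remain.

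**5. Power at one SD** (two-group t-test, one-sided 0.05):

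| Evaluable per group | Power |
|---|---|
| 15 | 84.8% |
| 17 | 88.6% |
| 19 | 91.6% |

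The loss slip costs 88.6 - 84.8 = 3.8 percentage points. The remaining gap to the nominal 90% arises because the table follows the normal approximation, which gives 89.8% at 17.

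**6. The other VR study in the background.** The section on clinical evaluation reports Fugl-Meyer 13.41 to 31.91 with VR, "compared to the group who received habitual occupational therapy (18 to 26.3"). The difference in change is (31.91 - 13.41) - (26.3 - 18) = 18.5 - 8.3 = 10.2 points, with baselines 18 - 13.41 = 4.59 points apart. No SD is given. If 12.23 is the SD of a single score and the pre-post correlation r is assumed, the SD of change is 12.23 x sqrt(2(1 - r)): 14.5 at r = 0.3 and 7.7 at r = 0.8. Power at 10.2 points with 17 per group then runs from about 64% to 98%, too wide to use as a benchmark.

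**The case against.** **The basis of 17 can be recovered.** The plan says the effect exceeds one SD, names the table and reproduces it; 3.16 does exceed 1, and using the last row is conservative if 38.6 were real. This stands. What is missing is the conversion to points and a target that is a genuine difference.

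**The tests are unaffected.** No planned ANOVA or Kruskal-Wallis comparison uses 38.6 as a margin. This also stands. A reader might infer that no result can be judged, or that the wrong figure left the trial underpowered; the documents support neither, since the size was set at one SD.

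**The pilot as a target.** A reader might infer that hundreds of patients per group are needed because the pilot differences are so small. With 13 and 10 patients, the pilot does not establish a firm target in either direction.

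**The SD wording.** 12.23 is the largest of the six Fugl-Meyer SDs in Table 1, so calling it the lowest looks wrong. But the translated phrase can be read as the smallest value that covers all the others, which is the maximum. The wording needs clarifying; it is not necessarily an error.

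**An impossible score.** On the 66-point upper-limb score, 38.60 + 38.6 = 77.2 exceeds the maximum. The plan also describes a 100-point motor base and a 226-point total, on which 77.2 is possible. The hypothesis names the upper limb but not the score, so impossibility cannot be asserted.

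**The fall from 90% to 85%.** It would be wrong to attribute all of this to the loss slip, as step 5 of the working shows.

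**Conclusion.** The point holds on three counts. First, 38.6 is used as a between-group difference but matches a control-group mean. No document states this origin; it is inferred from the exact match, from 12.23 coming from the same column, and from the absence of any reported difference near 38.6. Second, 17 per group corresponds to one SD, 12.23 points, and not to the stated effect. Third, 19 per group covers about 10.5% losses rather than 20%.

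The effect on power is modest: at 20% losses, 84.8% instead of 88.6% at one SD. This assumes equal groups, SD 12.23, a one-sided 0.05 test and a two-group t-test, which is the comparison behind the table, whereas the planned analysis is repeated-measures ANOVA or Kruskal-Wallis. The main fault is that the plan misstates the effect it hypothesises and is sized to detect. It must be corrected, because readers will rely on these figures.

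**What to change.** Issue a dated, disclosed correction that:

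- removes 38.6 as a difference from the Hypothesis, the Work Hypothesis and the Sample size section, and corrects both footnotes on its origin;
- states that 12.23 is the largest Fugl-Meyer SD in Table 1 and is an SD of baseline scores, not of change;
- states that 17 per group corresponds to an assumed difference of one SD (12.23 points), one-sided, with the pilot differences of 1.87 (change) and 2.47 (final) set beside it and their small numbers noted;
- states that 19 per group allows about 10% losses, and that if 20% are lost about 15 remain, with about 85% power at one SD;
- names the Fugl-Meyer score to which the hypothesis refers.

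Any power quoted at the 10.2-point difference should be omitted or shown as the range above with its assumed correlations.

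The cost is a few sentences and two footnotes. The stated power becomes slightly less favourable. No extra patients, redesign or change to the planned tests is needed. This corrects stated figures and should not be used to choose a new target effect afterwards.
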